## STATEMENT OF COMPLIANCE

The trial will be conducted in accordance with International Conference on Harmonisation Good Clinical Practice (ICH GCP), applicable United States (US) Code of Federal Regulations (CFR), and the terms and conditions of the contract. The Principal Investigators will assure that no deviation from, or changes to the protocol will take place without prior agreement from the funding agency and documented approval from the Institutional Review Board (IRB), except where necessary to eliminate an immediate hazard(s) to the trial participants. All personnel involved in the conduct of this study have completed Human Subjects Protection.

The protocol, informed consent form(s), recruitment materials, and all participant materials will be submitted to the IRB for review and approval. Approval of both the protocol and the consent form must be obtained before any participant is enrolled. Any amendment to the protocol will require review and approval by the IRB before the changes are implemented to the study. All changes to the consent form will be IRB approved; a determination will be made regarding whether a new consent needs to be obtained from participants who provided consent, using a previously approved consent form.

## 1 PROTOCOL SUMMARY

### 1.1 SYNOPSIS

**Title** Use of ProAir Digihaler in COPD - Characterization of inhalation metrics from a cohort of patient at-risk for an acute exacerbation of COPD (AECOPD) in an outpatient setting

**Study Description** The albuterol sulfate electronic multidose dry powder inhaler (Albuterol eMDPI) Digital System (DS) (ProAir® Digihaler®) is the first and only FDA approved inhaler rescue medication with a built-in sensor to detect and record inhaler use. The inhaler device measures peak inspiratory flow (PIF) and the app groups PIF into categories that can help to highlight potential patient inhaler technique errors. This study will deploy this product in COPD patients to establish foundational data on Digihaler metrics in a COPD population at greater risk for COPD exacerbations.

Adult subjects with COPD recruited from two sites (UNC and Wake Forest) will participate in a longitudinal study to collect data regarding the normal variation in Digihaler metrics (PIF, inhalation volume, # inhalations), a daily self-assessment asking “How are you feeling?” with responses provided on a Leikert scale as well as responses to a Digihaler metric algorithm-triggered digital automated questionnaire (DAQ) in a stable COPD population with history of an AECOPD, to assess correlations of Digihaler metrics to daily self-assessment and DAQ responses, correlations of self-reported to actual short acting beta agonist (SABA) use and symptoms, and the changes in inhaler parameters and SABA use around incidental AECOPD.

### Objectives

#### Primary Objective.

- To determine the variation in ProAir Digihaler metrics (PIF, inhalation volume, number of inhalation events) amongst COPD patients in the ambulatory setting.

**Secondary Objectives.**

- To determine the correlation of self-reported SABA use with actual SABA use collected by the ProAir Dihihaler.
- To determine the correlation of inhaler metrics (PIF, inhalation volume, number of inhalation events) with monthly CAT score domains.
- To determine the correlation of inhaler metrics (PIF, inhalation volume, number of inhalation events) with the daily daily self-assessment asking "How are you feeling?" with responses provided on a Leikert scale.

**Exploratory Objectives.**

- To determine the change in inhaler metrics in patients experiencing an AECOPD during study period.
- To determine the correlation of inhaler metrics (PIF, inhalation volume, number of inhalation events) with the Dihihaler metric algorithm-triggered DAQ.
- To describe COPD-related health-care resource utilization (HRU):
  - Number of COPD exacerbations-associated hospitalizations
    - Proportion of patients with 30-day COPD-related hospital re-admission
  - Number of COPD exacerbations-associated emergency room visits
    - Proportion of patients with 30-day COPD-related emergency room re-admission
  - SABA utilization
- To describe patient treatment/device satisfaction/ease of use.
- To describe patient APP satisfaction/ease of use.

**Study Design****Outcome Measures**

Multicenter 3-month observational study

Primary Outcome Measure:

1. Variability in Peak Inspiratory Flow (PIF) Measured via Dihihaler Device (Time Frame: Three months)
  - a. PIF is the maximal flow occurring during an inhalation effort, expressed in Liters/minute. Mean, standard deviation and coefficient of variation (calculated by dividing standard deviation of PIF by the mean of the PIF) of daily PIF measurement collected over three months will be calculated. PIF will be measured using the Dihihaler device.

Secondary Outcome Measures:

1. Correlation of Self-Reported Inhaler Use with Actual Inhaler Use (Time Frame: 3 months)
  - a. Correlation between self-reported inhaler use and actual inhaler use over three months will be calculated with Spearman rank-order correlation coefficient. Self-reported inhaler use will be determined with an investigator-

developed single question categorizing average use over the last four weeks with five groups (not at all, once a week or less, two or three times a week, one or two times a day, three or more times a day). Actual inhaler use will be directly measured via Digihaler device and categorized into one of the five groups described above.

2. Variability in Inhalation Volume Measured via Digihaler (Time Frame: Three months)

- a. Inhalation volume is the volume of air inspired during an inhalation effort, expressed in Liters. The mean, standard deviation and coefficient of variation (calculated by dividing standard deviation of inhalation volume by the mean of the inhalation volume) of daily inhalation volume measurements collected daily over three months will be calculated. Inhalation volume will be measured using the Digihaler device.

**Analysis Strategy**

The primary analysis will be descriptive, with analytical plans as defined above for each primary and secondary outcome.

Additional exploratory analysis will include linear regression (continuous) or negative binomial regression (count) of the clinical and demographic factors associated with inhaler from primary and secondary outcomes; descriptive statistics (mean, median, variance estimate and 95% confidence intervals) of number of inhalation events, correlation of inhaler metrics (PIF, inhalation volume, number of inhalation events) with CAT score, correlation of inhaler metrics (PIF, inhalation volume, number of inhalation events) with daily self-assessment asking “How are you feeling?” with responses provided on a Leikert scale, correlation of inhaler metrics (PIF, inhalation volume, number of inhalation events) with responses to metric algorithm-triggered DAQ; change in inhaler metrics (during the 7 days after and/or leading into hospitalized AECOPD or home treatment of a moderate AECOPD defined by a prescription for steroids and/or antibiotics); descriptive statistics (proportion, 95% CI) of COPD-associated hospitalizations and emergency room visits as well as SABA utilization; and patient satisfaction will be assessed with a post-study survey.

**Target Population**

**Inclusion Criteria:**

- Age >40 years old
- History of cigarette smoking >=10 pack-years
- Established COPD defined as physician diagnosis along with spirometry confirmation (post-BD FEV1/FVC<0.70) within the last two years and an FEV1 ≤80% predicted
- Regular albuterol use (defined as at least one puff weekly for each of the last four weeks)
- Currently non-hospitalized

- Medical records confirmed history of two moderate AECOPD (defined as use of antibiotic or steroids to treat clinical event consistent with AECOPD) or one severe AECOPD (defined as ED/hospital visit) in prior 12 months
- Access to smartphone, tablet or computer and internet
- Willingness to switch current rescue inhaler/device to ProAir Dihihaler

**Exclusion Criteria:**

- Allergy or inability/contraindication to use Albuterol Sulfate
- Any condition that, in the opinion of the site investigator, would compromise the subject's ability to participate in the study

**Study Cohort**

Patients (n=60) with documented COPD and a history of two moderate or one severe AECOPD in prior 12 months.

**Phase**

This is an early-stage preparatory study that paves the way for this line of research moving forward into multicenter clinical trials.

**Research Sites**

This study will enroll patients who are currently followed at The University of North Carolina at Chapel Hill (N=30) or Wake Forest University in Winston-Salem, NC (N=30). Participants will be recruited from existing clinical pools at both sites including COPD registries, virtual and in-person outpatient clinics (routine or post-hospital discharge).

**Description of Study****Intervention:**

In light of the COVID pandemic, this study is designed to be conducted entirely virtually to minimize any potential interruptions related to COVID. After identification and consenting, participants will be mailed the ProAir Dihihaler (provided by Teva). The study coordinator will contact the participant to ensure set-up and correct usage. Participants will be asked to use the ProAir Dihihaler as their primary mode of SABA therapy as they would in usual treatment and indicated in the product package insert and Instructions for Use. They will be provided a COPD Action Plan to ensure they have appropriate instructions to handle a possible AECOPD. They will answer a daily self-assessment asking "How are you feeling?" with responses provided on a Leikert scale on the DAQ App, as well as Dihihaler metric algorithm-triggered DAQ on the DAQ app. The DAQ will collect yes/no responses to questions focused on change in respiratory symptoms, sleep disturbances, daily activity limitation, and anxiousness.. The participants will be contacted once per month to collect CAT score and self-reported average albuterol use over the preceding month. They will also be asked about any AECOPD events requiring treatment with antibiotics and/or steroids or hospitalization in the prior month. Participants will be enrolled for three months duration. All individuals will be provided three inhalers at enrollment. In the event their ProAir Dihihaler does not last three months, they will be prescribed another ProAir Dihihaler (provided by Teva).

**Study Duration:**

[figure not shown]
This study is intended to last 18 months.

**Participant Duration:**

There will be no in-person visits. Participants will undergo a virtual screening/enrollment visit, followed by an initial check-in call to ensure device set up within one week of receipt. They will then receive three monthly calls during study. In the event the participant has an AECOPD

within two weeks of end of study, they will be followed for 14 days after AECOPD resolution. Total participant duration is three months (+21 days to account for 14 days in event of AECOPD and seven day window at end of study).

## 1.2 SCHEMA

**Figure 1.2.1:** Timeline of planned study events.

## 1.3 SCHEDULE OF ACTIVITIES (SOA)

Procedures	Screening & Enrollment Virtual Visit	Confirmatory Phone Call	Phone visit #1	Phone visit #2	Phone visit #3
Time Window (days)	-21	0	30 $\pm$ 7	60 $\pm$ 7	90 $\pm$ 21
Informed consent	X				
Demographics	X				
Medical history	X				
Confirmation of Device Set-Up		X			
COPD Assessment Test	X		X	X	X
COPD Exacerbation History	X		X	X	X
Inhaler Use and Compliance	X		X	X	X
Adverse Event Assessment		X	X	X	X
Complete Case Report Forms (CRFs)	X	X	X	X	X

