The participants will be contacted once per month to collect CAT score and self-reported average albuterol use over the preceding month. They will also be asked about any AECOPD events requiring treatment with antibiotics or steroids in the prior month. If there is evidence during the calls of clinical deterioration by self report or an abrupt increase in CAT by > 4 units patients will be advised to contact their primary care or COPD provider.

Participants will be enrolled for three months duration. In the event the participant has an AECOPD within two weeks of end of study, they will be followed for 14 days after AECOPD resolution. Total participant duration is three months (+21 days to account for 14 days in event of AECOPD and seven day window at end of study). In the event their ProAir Digihaler does not last three months, they will be prescribed another device (provided by Teva). Hospital admission during the course of the study will not prohibit continued participation.

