#### 4.2 END OF STUDY DEFINITION

A participant is considered to have completed the study if he or she has completed all phases of the study including the last phone visit shown in the Schedule of Activities (SoA), Section 1.3.

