### 9.4 STATISTICAL ANALYSES

Below are the pre-specific outcome measures:

Primary Outcome Measure:

1. Variability in Peak Inspiratory Flow (PIF) Measured via Digihaler Device (Time Frame: Three months)
  - b. PIF is the maximal flow occurring during an inhalation effort, expressed in Liters/minute. Mean, standard deviation and coefficient of variation (calculated by dividing standard deviation of PIF by the mean of the PIF) of daily PIF measurement collected over three months will be calculated. PIF will be measured using the Digihaler device.

Secondary Outcome Measures:

1. Correlation of Self-Reported Inhaler Use with Actual Inhaler Use (Time Frame: 3 months)

- a. Correlation between self-reported inhaler use and actual inhaler use over three months will be calculated with Spearman rank-order correlation coefficient. Self-reported inhaler use will be determined with an investigator-developed single question categorizing average use over the last four weeks with five groups (not at all, once a week or less, two or three times a week, one or two times a day, three or more times a day). Actual inhaler use will be directly measured via Digihaler device and categorized into one of the five groups described above.
2. Variability in Inhalation Volume Measured via Digihaler (Time Frame: Three months)
  - a. Inhalation volume is the volume of air inspired during an inhalation effort, expressed in Liters. The mean, standard deviation and coefficient of variation (calculated by dividing standard deviation of inhalation volume by the mean of the inhalation volume) of daily inhalation volume measurements collected daily over three months will be calculated. Inhalation volume will be measured using the Digihaler device.

The primary analysis will be descriptive, with analytical plans as defined above for each primary and secondary outcome.

The primary analysis will be descriptive, with analytical plans as defined above for each primary and secondary outcome.

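### The Schedule of Activities lets the final call fall on day 69, while the text explains the same 21 days only as an addition to three months; the early limits need reconciling (minor).

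*Combined protocol and SAP*

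**What the plan says.** Section 1.3 gives the windows in one row: "Time Window (days) -21 0 30 $\pm$ 7 60 $\pm$ 7 90 $\pm$ 21". The columns are the screening and enrollment visit, the confirmatory call (day 0) and Phone visits #1, #2 and #3. The last window is symmetric and three times as wide as the two before it.

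The Participant Duration entry of the Synopsis explains the 21 days: "Total participant duration is three months (+21 days to account for 14 days in event of AECOPD and seven day window at end of study". Section 4.1 repeats this after stating the rule behind the 14 days. Enrollment lasts three months, and for participants whose exacerbation falls in the closing fortnight the rule is that "they will be followed for 14 days after AECOPD resolution".

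Section 4.2 defines a completer as someone who has "completed all phases of the study including the last phone visit shown in the Schedule of Activities (SoA), Section 1.3". It sets no minimum number of days.

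In Section 9.4 the primary outcome is "Variability in Peak Inspiratory Flow (PIF) Measured via Digihaler Device (Time Frame: Three months", and its mean, SD and coefficient of variation are "of daily PIF measurement collected over three months will be calculated". The first secondary outcome compares recorded use with a single self-report question "categorizing average use over the last four weeks with five groups".

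**The concern.** The schedule and the text share the number 21 but give it different directions. Follow-up after a late exacerbation can only lengthen participation, so it gives no reason to close three weeks early. The likeliest explanation is a plus sign entered as plus-or-minus, but coordinators work from the schedule.

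What depends on the last call is the information gathered by telephone:

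- **Exacerbations and hospitalizations.** These are asked about at the monthly calls (Synopsis, Sections 4.1 and 6.1.1). No later call is scheduled.
- **Adverse events.** Section 8.3.4 collects them mainly at the calls. Section 8.3.5 ends routine SAE reporting 24 hours after the final call, which would be day 70 after a day-69 call. Later SAEs are reportable only if a causal link to the drug is suspected.
- **Self-reported use and CAT.** Neither would be collected by telephone again after the last call.
- **Replacement.** Section 7.2 replaces participants who withdraw, so that 60 complete data sets are obtained. Someone closed on day 69 is a completer and would not be replaced.

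**Working it through.** **Inputs.** Visit windows come from Section 1.3. The 14-day and seven-day parts come from the Synopsis and Section 4.1. The four-week (28-day) recall comes from Section 9.4. Three months is taken as day 90 of the schedule, counted from the confirmatory call on day 0.

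**Step 1: reproduce the plan's own figure.** 14 + 7 = 21, which matches the stated extension.

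**Step 2: limits for Phone visit #3.**

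- Schedule: 90 − 21 = 69 to 90 + 21 = 111.
- Text as written (addition only): 90 to 90 + 21 = 111.
- Text with the seven days two-sided, as for visits #1 and #2: 90 − 7 = 83 to 90 + 7 + 14 = 111.

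The late limit is day 111 each time. On this day count, neither reading of the text gives day 69.

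**Step 3: consequences of each early limit.** Visit #2 may be as late as 60 + 7 = 67. The minimum gap is the earliest visit #3 minus 67. The shared recall is 28 minus that gap. The days with no matching self-report are 90 minus the earliest visit #3.

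| Earliest visit #3 | Share of 90 days | Minimum gap from visit #2 | Shared days of the two 28-day recalls | Days to day 90 without a matching self-report |
|---|---|---|---|---|
| 69 (schedule) | 69/90 = 76.7% | 69 − 67 = 2 | 28 − 2 = 26 | 90 − 69 = 21 |
| 83 (seven days two-sided) | 83/90 = 92.2% | 83 − 67 = 16 | 28 − 16 = 12 | 90 − 83 = 7 |
| 90 (text as written) | 100% | 90 − 67 = 23 | 28 − 23 = 5 | 0 |

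For comparison, the minimum gap between visits #1 and #2 is 53 − 37 = 16 days, the same as the day-83 row.

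**Step 4: does the device record end with the call?** No formula applies, so the sections are set side by side. Section 4.1 enrolls participants for three months. Section 6.1.1 describes automatic transfer from inhaler to app to server. Section 7.3 treats failure to reach someone by telephone and failure to transmit data as separate conditions. Section 4.2 makes the last call necessary for completion, but does not say that recording stops there. No section requires recording to continue after the call either. The plan is silent on this.

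**The case against.** A reader might infer that a participant can satisfy the three-month endpoint with 69 days of data, and that 21/90 = 23.3% of device days would be lost. The documents do not support that. It requires device recording to stop at the last call, which no section says, and enrollment for three months with passive transfer points the other way. What stands is that the plan does not say when recording ends.

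The two-day gap between visits #2 and #3 needs the latest permitted visit #2 and the earliest permitted visit #3. It also conflicts with the Synopsis and Section 4.1, which call for contact once a month. It is a permitted extreme, and the documents give no basis for saying how often it would occur.

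The effect on the analysis is limited. The primary outcome is a descriptive mean, SD and coefficient of variation, not a total that grows with days observed. No bias from a shorter record has been shown. Section 9.3 already admits anyone who completes baseline and the one-month call, Section 9.2 states that there is no power calculation, and exacerbation and health-care-use outcomes are exploratory. All of this stands and keeps the severity low. Even so, tolerating dropout differs from authorizing early closure through a scheduling window.

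Day 69 is 90 days after a screening visit held on day −21, so the early limit might be defended by counting from consent. But the inhaler is mailed only after consent, and the schedule itself numbers the final call as day 90 from day 0. That count would not give three months of device data. The timeline figure in Section 1.2 could not be read here and may bear on the intended limits.

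The late limit is also not fully settled. If an exacerbation began on day 90 and took more than seven days to resolve, 14 days of follow-up from resolution would pass day 111 (90 + 7 + 14 = 111). That is a separate loose end in the same wording.

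**Conclusion.** The inconsistency is real, and it affects conduct because completion is tied to a call that the schedule allows on day 69. The early limits differ by 21 days, or by 14 if the seven-day window is two-sided (83 − 69 = 14). The late limits agree.

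The consequence is unequal telephone follow-up among completers: up to 21 days without scheduled ascertainment of exacerbations, hospitalizations and adverse events, and up to 21 days of recorded use with no self-report to compare. Loss of PIF and inhalation-volume data is possible but not stated. The effect on the primary outcome is probably small, and eligibility for analysis is unchanged.

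This rests on day 90 standing for three months and day 0 being the confirmatory call. The figures are what the windows permit, not what sites are expected to do. Severity: minor.

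**What to change.** Reconcile Section 1.3 with the Synopsis and Section 4.1 by giving the early and late limits for Phone visit #3 separately:

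- 90 −0/+21, as the text is written; or
- 90 −7/+21, if the sponsor confirms that the seven-day window is two-sided.

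In either case, reserve the additional 14 days for the follow-up after a late exacerbation. The minimum gap between visits #2 and #3 then rises from 2 days to 23 or 16.

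Add one sentence to Section 4.2 saying that device data are collected for the full three months, to day 90, whenever the last call takes place. This matters most under −7/+21, where the call could still precede day 90.

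The cost is one table cell and one sentence in a minor amendment, plus slightly less freedom in scheduling the last call.

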## 2 INTRODUCTION

### 2.1 STUDY RATIONALE

The ProAir Digihaler is the first and only digital inhaler with a built-in sensor to detect inhaler use, measure inspiratory flow, and capture potential technique errors. This device has been studied in asthma, but little information is available regarding the measurement characteristics in COPD patients. This device has the potential to help assess SABA use as a marker of COPD control and identify inspiratory flow metrics representing the onset of an AECOPD. In order to inform these purposes, it is necessary to first characterize the normal variation in Digihaler metrics (PIF, inhalation volume, # inhalations) in a stable COPD population with history of AECOPD as well as assess the changes around incidental AECOPD and

correlations of self-reported with actual SABA use and COPD patient reported outcomes. The accompanying app also permits collection of a daily self-assessment asking “How are you feeling?” with responses provided on a Likert scale and responses to a Digihaler metric algorithm-triggered DAQ on the DAQapp. The DAQ will collect yes/no responses to questions focused on change in respiratory symptoms, sleep disturbances, daily activity limitation, and anxiousness.. Collecting these foundational data are the specific objectives of this proposal.

